#### 15.1.5. SERIOUS ADVERSE EVENTS (SAEs)

Serious adverse events (SAEs) as indicated by the investigator, will be obtained from the serious variable on the Adverse Events form in eSource. These AEs will be included in the unsolicited AE overview as well as in the unsolicited AE listing.

The following tables are planned for presentation for the Total Vaccinated Cohort:

- Overview of SAEs by dose:
  - o Number and percentage (%) of subjects in each of the following categories:
    - Any SAE.
    - SAE with outcome of death.
    - Severe (grade 3) SAE.
    - Related SAE.
    - Related SAE with outcome of death. Severe (grade 3) related SAE.
  - o Percentage (%) of subjects will be calculated relative to the total number of subjects in the relevant analysis cohort per treatment group.
  - o A 95% confidence interval (CI) for the proportion of subjects with AEs in each category will be obtained by using the exact binomial option.
  - o Subjects with multiple events in each category are counted only once in each category.

The following by dose (Total, EBO-Z, Nimenrix) tables are similar to those described for the unsolicited AEs in Section 15.1: Unsolicited Adverse Events:

- Incidence of SAEs.
- Incidence of SAEs by severity.
- Incidence of related SAEs by severity.
- Incidence of SAEs by relationship.
- Number and percentage of SAEs including the number of events.
- Number and percentage of related SAEs including the number of events.

For all SAEs the SOC's will be sorted by descending frequency of the total number of subjects with at least one SAE in the overall category. Within each SOC, PTs will be sorted by descending frequency of the total number of subjects with at least one SAE in each category. Ties will be sorted alphabetically.

#### 15.1.5.1. Serious Adverse Events (SAEs) with Outcome of Death

Adverse events (AEs) with outcome of death are those events which are recorded as resulting in death on the Adverse Events form in eSource. These AEs will be included in the unsolicited AE overview and also indicated in the SAE listing.

#### 15.1.6. ADVERSE EVENT (AE) POST-VACCINATION REPORTING WINDOW

All AE incidence tables will only include AEs (SAEs, AESIs and unsolicited AEs) which occurred within the protocol defined post-vaccination reporting window, as defined in Table 5: Unsolicited Adverse Event (AE) Postvaccination Reporting Windows, below. All AE listings will include all the AEs reported, regardless whether it was reported within the reporting window. All AEs reported outside the reporting window will be indicated in the listing.

Table 5: Unsolicited Adverse Event (AE) Post-vaccination Reporting Windows

Adverse Event Type	Post-vaccination Reporting Window
SAEs	Through data cut-off
AESIs	7-day window following Day 0
Unsolicited AEs	30-day window following each vaccination

## 15.2. SOLICITED ADVERSE EVENTS (AEs)

Solicited AEs will not be coded by data management and as per coding will be assigned based on the information provided in Table 6: Solicited Adverse Events MedDRA Coding.

For a given subject, missing or non-evaluable measurements will not be replaced. Therefore the analysis of the solicited symptoms will include only vaccinated subjects with documented safety data (that is; symptom screen completed after the vaccination). More specifically the following rules will be used:

- Subjects who documented the absence of a solicited symptom after a vaccination will be considered not having that symptom after that vaccination.
- Subjects who documented the presence of a solicited symptom and fully or partially recorded daily measurement over the solicited period will be included in the summaries for that vaccination and classified according to their maximum observed daily recording over the solicited period.
- Subjects who documented the presence of a solicited symptom after a vaccination without having recorded any daily measurement will be assigned to the lowest intensity category for that vaccination (that is; 37.5°C for fever or grade 1 for other symptoms).

Document: CHAD3-004-EBO-Z\_Interim\_Final\_SAP\_v2\_0

Author: PPD Version Number: 2.0 Version Date: 14JUN2017

Template No: CS\_TP\_BS016 – Revision 3

Reference: CS\_WI\_BS005

Effective Date: 01May2012

- Vaccinations without symptom sheets documented will be excluded.

The following AE variables, as presented in the planned TLF shells, will be collected on the Solicited Adverse Events Local Signs and Symptoms form in eSource:

- Any signs or symptoms between Day 0 and Day 6:
  - o Yes. o No.
- Per day (Day 0 to Day 6) presence of each of the following signs or symptoms:
  - o Redness:  
Diameter measurement (mm).
  - o Swelling:  
Diameter measurement (mm).
  - o Pain:  
Intensity (0 to 3).Per sign or symptom:
- Ongoing after Day 6:
  - o Yes:  
Maximum diameter/intensity after Day 6.  
End date after Day 6. o No.
- Did the subject discontinue due to the event:
  - o Yes.
  - o No.

The following AE variable, as presented on the planned TLFs, will be collected on the Solicited Adverse Events General Signs and Symptoms form in eSource:

- Any signs or symptoms between Day 0 and Day 6:
  - o Yes.
  - o No.
- Per study day (Day 0 to Day 6) presence of each of the following signs or symptoms for children aged 6 to 17 years of age:
  - o Fever:  
Temperature reading (°C).
  - o Headache:  
Intensity (0 to 3).
  - o Fatigue:  
Intensity (0 to 3).
  - o Gastrointestinal symptoms: Intensity (0 to 3).

---

Document: CHAD3-004-EBO-Z\_Interim\_Final\_SAP\_v2\_0  
Author: PPD Version Number: 2.0 Version Date: 14JUN2017

Template No: CS\_TP\_BS016 – Revision 3  
Effective Date: 01May2012

Reference: CS\_WI\_BS005

- Per study day (Day 0 to Day 6) presence of each of the following signs or symptoms for children aged 1 to 5 years of age:
  - o Fever:  
Temperature reading (°C).
  - o Loss of Appetite:  
Intensity (0 to 3).
  - o Drowsiness:  
Intensity (0 to 3).
  - o Irritability/Fussiness:  
Intensity (0 to 3).

Per sign or symptom:

- Ongoing after Day 6:
  - o Yes:  
Maximum reading/intensity after Day 6.  
End date after Day 6. o  
No.
- Did the subject discontinue due to the event:
  - o Yes. o No.
- Relationship to study vaccine:
  - o Yes.
  - o No.

The following diary card variable will be collected on the Diary Card Review form in eSource:

- Did the field worker/site personnel return the diary card:
  - o Yes. o No.

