### Reactogenicity and Safety

- Handling of missing data: subjects who missed reporting symptoms (unsolicited or concomitant medications) will be treated as subjects without symptoms (unsolicited or concomitant medications, respectively). In case of significant non-compliance of study procedures for reporting symptoms, the analysis plan will be reassessed to ensure more accurate reporting of study data by further analysis.
- For the analysis of solicited symptom, missing or non-evaluable measurements will not be replaced. Therefore the analysis of the solicited symptoms based on the TVC will include only subjects/doses with documented safety data.

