#### 2.1.2. PRIMARY ENDPOINTS

- Occurrence of each solicited local and general adverse event (AE), during a 7-day follow-up period after each vaccination (that is, the day of vaccination and 6 subsequent days), in all subjects, in both groups.
- Occurrence of any unsolicited AE, during a 30-day follow-up period after each vaccination (that is, the day of vaccination and 29 subsequent days), in all subjects, in both groups.
- Occurrence of haematological (complete blood count [CBC], including differential count and platelet count) and biochemical (alanine aminotransferase [ALT], creatinine) laboratory abnormalities at Screening, Day 3, Day 6, Day 30, Month 6, Month 6 + 6 days, Month 6 + 30 days and Month 12 in all subjects, in both groups.
- Occurrence of clinical symptoms of thrombocytopenia (AE of specific interest), during a 7-day follow-up period after vaccination at Day 0 (that is, Day 0 up to Day 6), in all subjects, in both groups.
- Occurrence of any serious adverse event (SAE), in all subjects, in both groups.

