## 3.3. CHANGES TO ANALYSIS FROM PROTOCOL

None.

Document: CHAD3-004-EBO-Z\_Interim\_Final\_SAP\_v2\_0

Author: PPD Version Number: 2.0 Version Date: 14JUN2017

Template No: CS\_TP\_BS016 – Revision 3

Reference: CS\_WI\_BS005

Effective Date: 01May2012

Copyright © 2012 Quintiles Transnational Corp. All rights reserved.

The contents of this document are confidential and proprietary to Quintiles Transnational Corp. Unauthorised use, disclosure or reproduction is strictly prohibited.

---

Document: CHAD3-004-EBO-Z\_Interim\_Final\_SAP\_v2\_0  
Author: PPD Version Number: 2.0 Version Date: 14JUN2017

Template No: CS\_TP\_BS016 – Revision 3  
Effective Date: 01May2012

Reference: CS\_WI\_BS005

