### 7.3. MISSING DATA

Missing safety data will not be imputed. For handling of partial or missing AE start dates, refer to Section APPENDIX 2: Partial Date Conventions.

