#### 15.2.2.1. Severity

Severity will be derived based on the intensity grading:

- Mild: Intensity grade of 1.
- Moderate: Intensity grade of 2.
- Severe: Intensity grade of 3.

In addition, for the intensity it can also be reported as the following:

---

Document: CHAD3-004-EBO-Z\_Interim\_Final\_SAP\_v2\_0  
Author: PPD Version Number: 2.0 Version Date: 14JUN2017

Template No: CS\_TP\_BS016 – Revision 3  
Effective Date: 01May2012

Reference: CS\_WI\_BS005

- Redness:
  - o Unknown. o Uninterpretable.
- Swelling, and fever:
  - o Unknown.

Severity is therefore classed as unknown, uninterpretable, mild, moderate or severe (increasing severity). If there are any missing intensities at the time of the analysis, those will be summarised in the unknown category.

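### SAP v2 15.2 assigns unrecorded solicited-symptom intensities to the mildest grade, against the no-replacement rule and the SAP's own unknown category, so the severity tables conceal missing grades

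*SAP*

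**What the plan says.** The protocol's rule on derived data for reactogenicity and safety (11.6) is: "For the analysis of solicited symptom, missing or non-evaluable measurements will not be replaced". It concludes that only subjects or doses with documented safety data enter the solicited analysis.

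SAP v2 15.2 opens the same way: "For a given subject, missing or non-evaluable measurements will not be replaced". It then lists specific rules. The third covers a child whose symptom is documented as present but who has no measurement on any day. Such a child, "without having recorded any daily measurement will be assigned to the lowest intensity category for that vaccination", receives "37.5°C for fever or grade 1 for other symptoms".

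Three other places in SAP v2 bear on the same record:

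- 7.3 (Missing Data): "Missing safety data will not be imputed".
- 15.2.2.1 (Severity): "If there are any missing intensities at the time of the analysis, those will be summarised in the unknown category". This section also keeps an uninterpretable category for redness.
- 3.3, headed "CHANGES TO ANALYSIS FROM PROTOCOL", contains only the word None.

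The relevant primary endpoint (2.1.2) is "Occurrence of each solicited local and general adverse event (AE), during a 7-day follow-up period after each vaccination". It is a yes/no outcome. Severity enters through the tabulations: protocol 11.8 asks for Grade 3 solicited events with exact 95% CIs, and SAP v2 15.2.2 plans an overview with Grade 3 rows and an incidence table by severity. The overview's denominator is subjects with returned diary cards. SAP v1 contains the same conflict between 7.3, 15.2 and 15.2.2.1.

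**The concern.** The plan gives two destinations for one record: mild under 15.2, unknown under 15.2.2.1. Two programmers following the SAP could produce different severity tables. The first destination is also a replacement of the kind that protocol 11.6, the opening of 15.2 and 7.3 exclude, and it is not declared in 3.3.

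The substance matters more than the wording. A child known to have reacted, but whose reaction was never graded, is reported as a confirmed mild case. A reader of the severity table cannot see that the grade was unobserved and cannot work out how high the Grade 3 rate might be. This kind of missingness is partly foreseen: both documents expect that redness on darkly pigmented skin may not be measurable, and 15.2 does not say whether an uninterpretable entry counts as a recorded measurement.

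Under SAP v2 4.2 the analysis team is unblinded at the interim analysis. A choice between two written rules should not remain open for the final analysis.

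**Working it through.** **Reproducing the plan's own method.** Protocol Table 22 uses exact (Clopper-Pearson) 95% intervals with n = 300. For 15 events this gives 15/300 = 5.00% (2.83 to 8.11), as printed; all seven rows of the table reproduce. No figure in the documents depends on the missing-intensity rule.

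**Inputs for an illustration.** Group size n = 300 comes from protocol 11.4. The rest is assumed, because the documents give no rate of missing intensity: 100 children with a given symptom, 90 of them graded, 18 recorded as Grade 3, and u = 10 with the symptom but no grade. All 300 are taken to have returned diary cards, and the overview denominator is taken to apply to the severity tables.

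**The two SAP rules compared.**

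| Quantity | 15.2 rule (grade 1) | 15.2.2.1 rule (unknown) |
|---|---|---|
| Any grade | 100/300 = 33.3% | 100/300 = 33.3% |
| Grade 3 | 18/300 = 6.0% (3.6 to 9.3) | 18/300 = 6.0% (3.6 to 9.3) |
| Mild | observed mild + 10 | observed mild |
| Intensity shown as unknown | 0 | 10 |

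The choice between the rules moves u children between mild and unknown. It changes neither the any-grade count nor the Grade 3 count, its denominator or its interval. What the unknown row adds is sight of u, from which the possible range can be read.

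**Bounds on Grade 3.** The lower bound is 18/300, if none of the u children was Grade 3. The upper bound is (18 + u)/300, if all were.

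| u (assumed) | Reported under 15.2 | Upper bound (exact 95% CI) |
|---|---|---|
| 1 | 6.0% | 19/300 = 6.3% (3.9 to 9.7) |
| 3 | 6.0% | 21/300 = 7.0% (4.4 to 10.5) |
| 6 | 6.0% | 24/300 = 8.0% (5.2 to 11.7) |
| 10 | 6.0% | 28/300 = 9.3% (6.3 to 13.2) |

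If the ungraded children resemble the graded ones, 10 × 18/90 = 2 of them would be Grade 3, giving 20/300 = 6.7%.

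**Direction by symptom.** In SAP v2 Appendix 4, redness or swelling at 13 to 17 years is Grade 0 up to 20 mm and Grade 1 only above 20 mm. For that stratum grade 1 is not the lowest category on the scale, so the 15.2 rule can raise a child's grade, and its two descriptions of the assigned value disagree. In the two younger strata Grade 1 starts above 0 mm, and for fever 37.5°C is the bottom of Grade 1, so there the rule assigns the lowest positive grade.

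**The case against.** The strongest defence is that the two SAP rules can be read in sequence: 15.2 deals with one specific case, a documented symptom with no daily measurement, and 15.2.2.1 takes whatever is still missing. On that reading the no-replacement sentence is about who enters the analysis, and these children have documented data. The SAP states no such order, however, and even in sequence a missing grade is still replaced by a value.

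Several other points on that side stand:

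- A reader might infer that the primary endpoint is biased. The documents do not support that. The endpoint is occurrence, and the child is counted as having the symptom under either rule.
- A reader might infer that the rule lowers the Grade 3 rate compared with using the unknown category. It does not: the figure is 18/300 both ways. The understatement is relative to the unobserved truth.
- A reader might want to base Grade 3 on children with a known grade, including those without the symptom. In the illustration that is 18/(200 + 90) = 18/290 = 6.2%, which does not recover 6.7%, and it departs from the returned-diary-card denominator in 15.2.2.
- A reader might infer a uniformly downward bias. Redness and swelling at 13 to 17 years are an exception.
- The affected group may be small. Protocol 5.6.14.1 has an investigator or field worker complete the card daily for 7 days, a child qualifies only with no measurement on any of them, and queries are to be resolved before analysis. Protocol 11.6 also calls for the analysis plan to be reassessed if reporting non-compliance is significant.
- All analyses are descriptive, and the rule is the same in both groups.

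**Conclusion.** The point holds for the severity tables. SAP v2 15.2 contains a replacement rule that conflicts with protocol 11.6, with its own opening sentence, with 7.3 and with 15.2.2.1, and 3.3 does not declare it. Its effect is to turn unobserved intensities into confirmed mild cases, to hide their number, and to make the reported Grade 3 rate a lower bound as far as these children are concerned.

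The size cannot be fixed from the documents. With u ungraded children in a group of 300, the Grade 3 rate could be higher than reported by up to u/300: 0.3 percentage points for one child, 3.3 points for ten. The example of 6.0% against at most 9.3% rests on assumed counts, and daily follow-up may keep the real gap well below that. The primary occurrence endpoint is not in question.

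**What to change.** In SAP v2:

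1. Delete the lowest-intensity rule from 15.2.
2. Count a child with a documented symptom and no recorded grade in the any-grade row.
3. Show that child's intensity as unknown, or as uninterpretable for redness where that was reported, as 15.2.2.1 already provides.
4. Keep returned diary cards as the denominator, and do not introduce a known-grade denominator.
5. Add one sensitivity line per severity table that counts unknown intensities as Grade 3. In the illustration it would read 28/300 = 9.3% beneath the observed 18/300 = 6.0%.

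If the sponsor prefers to keep the grade 1 rule, it should be declared in 3.3 as a change from protocol 11.6 and reconciled with 7.3 and 15.2.2.1, and its wording settled for redness and swelling at 13 to 17 years.

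The cost is one deleted sentence, a short clarification and one extra line per severity table. No further data are needed.

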#### 15.2.1. DERIVATIONS

Based on the aforementioned variables, the following variables will be derived:

- End date after Day 6 relative day:
  - o Calculated relative to the most recent vaccination (refer to Section 6.1: Reference Start Date and Relative Day).
- Duration of solicited sign or symptom (refer to Section 6.7.3: Duration):
  - o If ongoing after Day 6:  
End date/day: End date after Day 6 as recorded in eSource.

Document: CHAD3-004-EBO-Z\_Interim\_Final\_SAP\_v2\_0  
Author: PPD Version Number: 2.0 Version Date: 14JUN2017

Template No: CS\_TP\_BS016 – Revision 3  
Effective Date: 01May2012

Reference: CS\_WI\_BS005

Start date/day: Start date of sign or symptom (derived from the first study day where sign or symptom is present relative to the study vaccination date). o If not ongoing after Day 6:

End date/day: Last date of sign or symptom (derived from the study day where sign or symptom is present relative to the study vaccination date).

Start date/day: Start date of sign or symptom (derived from the first study day where sign or symptom is present relative to the study vaccination date).

- Relationship to study vaccine for local solicited signs or symptoms:
  - o All local signs or symptoms will be regarded as related to study vaccine.
- Intensity for fever, redness and swelling:

Refer to APPENDIX 4: Solicited Adverse Event (AE) Intensity Grading, for the required intensity grade assignment for fever, redness and swelling.

- Dose at onset:
  - o Dose at onset will be assigned for all solicited AEs and is defined as the most recent dose prior to the onset of the AE:
    - EBO-Z:
      - Day 0.
      - Month 6.
    - Nimenrix:
      - Day 0.
      - Month 6.

---

Document: CHAD3-004-EBO-Z\_Interim\_Final\_SAP\_v2\_0  
Author: PPD Version Number: 2.0 Version Date: 14JUN2017

Template No: CS\_TP\_BS016 – Revision 3  
Effective Date: 01May2012

Reference: CS\_WI\_BS005

- MedDRA System Organ Class as well as Preferred Term will be assigned based on Table 6: Solicited Adverse Events MedDRA Coding, below.

Table 6: Solicited Adverse Events MedDRA Coding

Solicited AE	MedDRA System Organ Class	MedDRA Preferred Term
Redness	Skin and subcutaneous tissue disorders	Erythema
Swelling	General disorders and administration site conditions	Swelling
Pain	General disorders and administration site conditions	Pain
Fever	General disorders and administration site conditions	Pyrexia
Headache	Nervous system disorders	Headache
Fatigue	General disorders and administration site conditions	Fatigue
Gastrointestinal Symptoms	Gastrointestinal disorders	Gastrointestinal disorder
Loss of Appetite	Metabolism and nutrition disorders	Decreased appetite
Drowsiness	Nervous system disorders	Somnolence
Irritability/Fussiness	Psychiatric disorders	Irritability

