**(Amended 06 May 2015.)**

The percentage of subjects with at least one local AE (solicited and unsolicited), with at least one general AE (solicited and unsolicited) and with any AE during the solicited follow-up period will be tabulated with exact 95% CI. The same calculations will be performed for symptoms rated as Grade 3.

The percentage of subjects reporting each individual solicited local and general AE during the solicited follow-up period will be tabulated with exact 95% CI. The same tabulation will be performed for Grade 3 AEs and for AEs with relationship to vaccination.

Duration and prevalence of fever will be presented.

The verbatim reports of unsolicited symptoms will be reviewed by a physician and the signs and symptoms will be coded according to the Medical Dictionary for Regulatory Activities (MedDRA). The percentage of subjects with at least one report of unsolicited AE classified by the MedDRA and reported up to 29 days after vaccination will be tabulated with exact 95% CI. The same tabulation will be performed for Grade 3 unsolicited AEs and for unsolicited AEs with a relationship to vaccination.

At each haematology/ biochemistry sampling time point, by study group, individual haematological and biochemical values will be presented as number of subjects out of range (above and below normal range) and tabulated by toxicity grading (refer to [APPENDIX C](#)). In addition, changes from baseline (median/ interquartile range) will be presented.

SAEs *and AEs of specific interest (clinical symptoms of thrombocytopenia)* will be described in detail.

*(Amended 06 May 2015.)*

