### 6.7.3. DURATION

- Duration = End Date/Day – Start Date/Day + 1.
- The start and end date/days are defined in each of the relevant sections where the duration calculation is required.

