#### 15.2.2. ALL SOLICITED ADVERSE EVENTS

The following listing is planned for presentation for the Total Vaccinated Cohort:

- Solicited AEs.

The following tables are planned for presentation for the Total Vaccinated Cohort:

- Overview of Solicited AEs:
  - Number and percentage (%) of subjects in each of the following categories:
    - Solicited AE.
    - Solicited severe (grade 3) AE.
    - Solicited related AE.
    - Solicited severe (grade 3) related AE.
    - Solicited local AE.

Document: CHAD3-004-EBO-Z\_Interim\_Final\_SAP\_v2\_0  
 Author: PPD Version Number: 2.0 Version Date: 14JUN2017

Template No: CS\_TP\_BS016 – Revision 3  
 Effective Date: 01May2012

Reference: CS\_WI\_BS005

- Severe (grade 3) solicited local AE.
- Solicited general AE.
- Severe (grade 3) solicited general AE.
- Related solicited general AE.
- Severe (grade 3) related solicited general AE.
- Solicited AE leading to premature study withdrawal.
- Severe (grade 3) solicited AE leading to premature study withdrawal.
- Related solicited AE leading to premature study withdrawal.
- Severe (grade 3) related solicited AE leading to premature study withdrawal.
- o Percentage (%) of subjects will be calculated relative to the total number of subjects in the relevant analysis cohort, per treatment group with returned diary cards.
- o A 95% confidence interval (CI) for the proportion of subjects with AEs in each category will be obtained by using the exact binomial option.
- o Subjects with multiple events in each category are counted only once in each category.
- Incidence of solicited AEs:
  - o Number and percentage (%) subjects with solicited AEs summarised by category and sign or symptom.
- Incidence of solicited AEs by severity:
  - o Number and percentage (%) subjects with solicited AEs summarised by category, sign or symptom and severity.
  - o This table will be repeated for related solicited AEs (including general solicited AEs only).
- Incidence of solicited AEs by relationship:
  - o Number and percentage (%) subjects with solicited AEs summarised by category, sign or symptom and relationship.
- Duration of fever (days):
  - o Descriptive statistics for the duration of fever will be provided, based on all subjects with at least one fever event reported.
- Onset Day of Fever during 7-day Follow-up Period After Vaccination on Day 0

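### Fever duration is a first-to-last span, so fever-free or unrecorded days between separate febrile days are counted as fever, which overstates the mean and upper tail of the fever-duration table

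*SAP*

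**What the plan says.** Protocol 11.8 requires that "Duration and prevalence of fever will be presented" and defines neither term. SAP v2 section 6.7.3 gives the general formula, "Duration = End Date/Day – Start Date/Day + 1", and section 15.2.1 supplies the two dates for solicited symptoms:

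- **Start:** "Start date/day: Start date of sign or symptom (derived from the first study day where sign or symptom is present".
- **End, not ongoing after Day 6:** "End date/day: Last date of sign or symptom (derived from the study day where sign or symptom is present". The bracket omits the word last, but the phrase before it makes the meaning clear.
- **End, ongoing after Day 6:** "End date/day: End date after Day 6 as recorded in eSource".

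SAP v1 has the same rule in the same sections. Neither version splits separate episodes or removes days without the symptom.

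The data to see gaps are collected. Section 15.2 has "Per study day (Day 0 to Day 6) presence of each of the following signs or symptoms for children aged 6 to 17" years, with a parallel list for ages 1 to 5, and for fever each day carries a "Temperature reading (°C"). The same section keeps children whose daily record is only partly complete and does not replace missing measurements.

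The measure is used in section 15.2.2: "Descriptive statistics for the duration of fever will be provided, based on all subjects with at least one fever event reported". The further fever table and figure added in SAP v2 use only the earliest day of onset.

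**The concern.** A reader of a fever-duration table will take the figure as days with fever. Under this rule it is the distance between the outermost febrile days, and the SAP does not label it so. Two isolated febrile days become one long fever, and an unrecorded day between two febrile days also counts as fever.

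Gaps are plausible here. The fever threshold is low (37.5 °C), and Protocol 1.2.2.1 describes the regions as malaria-endemic and says that infection may affect the safety evaluation. Safety and reactogenicity is the primary objective. No planned summary would show the gaps: the other fever outputs use first onset only, so a reader would have to go to the listing of solicited events. The measure also differs from persistence in the holding rules of Protocol 9.10, which count consecutive days.

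**Working it through.** **1. The rule on example patterns.** This needs no assumption.

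| Febrile days | SAP duration | Days with fever | Longest run |
|---|---|---|---|
| 0 only | 0 − 0 + 1 = 1 | 1 | 1 |
| 0, 1 | 1 − 0 + 1 = 2 | 2 | 2 |
| 1, 4 | 4 − 1 + 1 = 4 | 2 | 1 |
| 0, 5 | 5 − 0 + 1 = 6 | 2 | 1 |
| 0, 6 | 6 − 0 + 1 = 7 | 2 | 1 |
| 0, 1, 6 | 6 − 0 + 1 = 7 | 3 | 2 |

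Single and adjacent febrile days are unaffected. For two febrile days within Days 0 to 6, the largest excess is 7 − 2 = 5 days.

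**2. Size of the effect.** The documents state no fever rate or duration, so there is no planned figure to reproduce and the inputs are assumptions: background fever with probability b on each of 7 days, independent between days, and a one-day vaccine fever on Day 0 with probability v. Write q = 1 − b.

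- P(any fever) = 1 − (1 − v)q^7.
- Mean febrile days among febrile children = [v + (1 − v)b + 6b] / P(any fever).
- Mean span among febrile children = 1 + S / P(any fever), where S is the sum over d = 1 to 6 of (1 − q^(7−d)) × (1 − (1 − v)q^d).

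For b = 0.03 and v = 0.3:

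- P(any fever) = 1 − 0.7 × 0.808 = 0.434.
- Mean febrile days = (0.3 + 0.021 + 0.18) / 0.434 = 1.15.
- S = 0.0536 + 0.0482 + 0.0414 + 0.0332 + 0.0236 + 0.0125 = 0.2126, so mean span = 1 + 0.2126 / 0.434 = 1.49.

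| b | v | Mean febrile days | Mean span | Excess |
|---|---|---|---|---|
| 0.01 | 0 | 1.03 | 1.08 | 0.05 |
| 0.03 | 0 | 1.09 | 1.24 | 0.15 |
| 0.03 | 0.3 | 1.15 | 1.49 | 0.34 |
| 0.05 | 0.3 | 1.24 | 1.74 | 0.49 |

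(Excesses are from unrounded means.) With b = 0 and unbroken vaccine fever, the excess is zero.

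**3. Quartiles.** Over 27 scenarios (b = 1, 3, 5%; v = 0, 10, 30%; early fever of 1, 2 or 3 days from Day 0), the median and Q3 are the same for the span and the day count in every one.

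**4. Clustered background.** Suppose background fever comes in three-day episodes, each starting with probability 1% on each of Days 0 to 6, so that close to 3% of children are febrile per day from Day 2 on. The excess then falls from 0.34 to 0.13 day at v = 0.3, and from 0.15 to 0.01 day at v = 0.

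**5. Direction by arm.** Early fever now starts on Day 0 or Day 1 with equal probability and lasts L consecutive days; b = 0.02 in both arms.

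| L | Excess, v = 0 | Excess, v = 0.3 |
|---|---|---|
| 1 | 0.100 | 0.206 |
| 2 | 0.100 | 0.141 |
| 3 | 0.100 | 0.090 |
| 4 | 0.100 | 0.053 |

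Unequal background also reverses the order: with L = 1, v = 0.3 and b = 0.01 give 0.11 day, while v = 0.05 and b = 0.05 give 0.30 day.

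**The case against.** Onset to last day present is a pre-specified measure, identical in both SAP versions, and the protocol does not say that duration means febrile days. That stands: the span is a legitimate measure, and the fault is that it is unlabelled and stands alone.

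The effect is modest. Quartiles barely move, and independent background days favour gaps. Malaria is tested for and treated before entry (Protocol 5.6.2), and fever or acute disease on the day postpones vaccination (5.6.9 and 6.6), which should lower background fever in the week. All this limits the size without removing the mechanism.

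A febrile-day count has its own bias: it treats an unrecorded day inside an episode as afebrile. That also stands, and is why such days should be shown rather than absorbed.

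SAP v2 was written after the interim analysis, at which the analysis team was unblinded (section 4.2). Replacing a safety derivation then would be open to question, and could make the final duration inconsistent with the interim one. This argues for adding rows beside the span, not substituting for it.

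Reach is limited. The summary is descriptive, and fever incidence, grade, relationship and onset day do not use duration.

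**Conclusion.** The point holds as a reporting defect in one descriptive safety table. That gaps are counted as fever follows from the SAP text alone. The size, about 0.05 to 0.5 day in the mean, rests on assumed background fever of 1% to 5% per day, independent between days, and one-day vaccine fever in 0% to 30%. It is smaller with clustered background fever and nil without gaps. The mean and upper tail are affected; the median and Q3 largely are not.

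A reader might infer that the overstatement is greatest in the ChAd3-EBO-Z arm, because that arm could have more early fever. The documents do not support this. They give no fever rate or timing by arm, and the order reverses when early fever lasts longer or background fever differs between arms. A reader might also be drawn to the share of children with a long duration, such as four days or more. The SAP plans descriptive statistics of duration and no such cut-off.

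**What to change.** In SAP 15.2.1, and in the fever-duration table of 15.2.2, keep the present derivation and label it first to last febrile day. Add, by arm:

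- the number of days with recorded fever on Days 0 to 6, plus the days from Day 7 to the recorded end date if the fever is ongoing after Day 6;
- the longest run of consecutive febrile days;
- the number of children with a gap between febrile days, shown separately for fever-free and unrecorded days.

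The cost is one extra derivation and a few table rows, with no new data and no change to the pre-specified measure. Two limits belong in a footnote: the febrile-day count treats unrecorded days as without fever, and days after Day 6 are known only through the recorded end date and are taken as continuous fever.
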